4.6.1.3 Reporting of serious adverse events

Investigators and other site personnel must inform appropriate AstraZeneca representatives of any SAE that occurs in the course of the study within 1 day (ie, immediately but no later than the end of the next business day) of when he or she becomes aware of it.

The AstraZeneca representative or delegate will work with the investigator to compile all the necessary information and ensure that the appropriate AstraZeneca Drug Safety Department receives a report by day one for all fatal and life-threatening cases and by day five for all other SAEs.

Follow-up information on SAEs must also be reported by the investigator within the same time frames.

If a non-serious AE becomes serious, this and other relevant follow-up information must also be provided to AstraZeneca or delegate within 1 day as described above. For a non-serious AE that become serious but which is not fatal or life-threatening a report should be received within 5 days.

All SAEs have to be reported, whether or not considered causally related to the investigational product or to the study procedure(s). All SAEs will be recorded in the case report form. The investigator and/or Sponsor are responsible for informing the IRB and/or the Regulatory Authority of the SAE as per local requirements.

5. STUDY MANAGEMENT

5.1 Monitoring

5.1.1 Study monitoring

The monitoring of this study will be performed in accordance with the principles of Good Clinical Practice (GCP) as laid out in the International Conference on Harmonisation (ICH) document “Good Clinical Practice: Consolidated Guideline”.

The specific requirements of the genetic part of the study will be discussed with the investigator(s) (and other personnel involved with the study).

5.1.2 Data verification

It is a pre-requisite of this study that the study monitor has direct access to source data for data verification. This will be done by comparing data from the CRFs with those in the subject’s medical notes (permission from the subject will be sought as part of the consent process). Such verification is an essential element of quality control, as it allows the rectification of transcription errors and omissions.

For this study no original data recorded on the CRF and regarded as source data.

Monitoring including source data verification should routinely be performed prior to the transfer of data to Data Management.

Source verification of the genetic consent of participating subjects will be performed and make sure that the investigational team is adhering to the specific requirements of the genetics aspects of the study

5.2 Audits and inspections

Authorised representatives of AstraZeneca, a regulatory authority, an Ethics Committee or an Institutional Review Board may visit the centre to perform audits or inspections, including source data verification. The purpose of an AstraZeneca audit or inspection is to systematically and independently examine all study-related activities and documents to determine whether these activities were conducted, and data were recorded, analysed, and accurately reported according to the protocol, GCP guidelines of the ICH and any applicable regulatory requirements. The investigator should contact AstraZeneca or delegate immediately if contacted by a regulatory agency about an inspection at his or her centre.

5.3 Training of staff

The principal investigator will maintain a record of all individuals involved in the study (medical, nursing and other staff). He or she will ensure that appropriate training relevant to the study is given to all of these staff, and that any new information of relevance to the performance of this study is forwarded to the staff involved.

Before the first subject is entered into the study the investigational staff will have an opportunity to discuss the procedures associated with the collection of blood samples, extraction of DNA and genetic testing with AstraZeneca personnel or delegate. The ethical considerations specific to genotyping and the importance of the informed consent process will be made clear. The requirements for the collections of the subjects' samples will also be made clear.

5.4 Changes to the protocol

Study procedures will not be changed without the mutual agreement of the principal investigator and AstraZeneca or delegate.

If it is necessary for the study protocol to be amended, the amendment and/or a new version of the study protocol must be notified to or approved by each IRB and in many countries also the local regulatory authority, before implementation. Local requirements must be followed.

If an administrative change is required, such a change must be notified to or approved by each IRB according to local requirements.

If a protocol amendment requires a change to a particular centre's Informed Consent Form, then AstraZeneca or delegate and the centre's IRB must be notified. Approval of the revised Master Informed Consent Form by AstraZeneca or delegate and by the IRB is required before the revised form is used.

AstraZeneca or delegate will distribute amendments and new versions of the protocol to each principal investigator(s) who in turn is responsible for the distribution of these documents to his or her IRB, and to the staff at his or her centre. The distribution of these documents to the regulatory authority will be handled according to local practice.

5.5 Study agreements

The principal investigator at each centre must comply with all the terms, conditions, and obligations of the study agreement for this study. In the event of any inconsistency between this protocol and the study agreement, this protocol shall prevail.

Specific reference to genetics should be included in the agreement. The contractual obligations should not include any additional payment for collecting the samples, unless special processing is required.

5.6 Study timetable and end of study

The study is expected to start _____ and to be completed by _____.

5.7 Data management

5.7.1 Case report forms

Data will be entered in the Web Based Data Capture (WBDC) system at the investigational site. The WBDC system will be authorized and approved by AstraZeneca and set up and maintained by QDS. Trained study personnel will be responsible for entering data on the observations, tests and assessments specified in the protocol into the WBDC system and according to the eCRF Instructions within agreed timelines. The eCRF Instructions will also provide the study site with data entry instructions. Data entered in the WBDC system will be immediately saved to a central database and changes tracked to provide an audit trail. When data have been entered, reviewed, edited and Source Data Verification (SDV) has been performed, the Principal Investigator will be notified to sign a hard copy of the eCRF signature page and send it to QDS for imaging. An electronic copy of the eCRF will be provided to the investigational site after the study database has been locked and will be archived at the investigational site.

Data checks will be run and data validation performed continuously by QDS. The investigator should answer any queries raised by AstraZeneca or QDS during the entire duration of the study including the clean-file process.

Adverse events and Medical/Surgical history will be classified according to the terminology of the Medical Dictionary for Regulatory Activities (MedDRA). Medications will be classified according to the AstraZeneca Drug Dictionary. All coding will be performed by the CRO and reviewed and approved at AstraZeneca R&D Wilmington.

It is the responsibility of the Investigator to complete Serious Adverse Event Form when applicable. It is the AstraZeneca monitor's responsibility to ensure that any Serious Adverse Event Form is fully completed.

5.7.2 Electronic data capture at bedside

During the study days, data will be captured electronically at bedside.

The Investigator will ensure that the captured data are correct before transferred to the central database. Any changes made during validation will be documented with a full audit trail within the WBDC application.

Any missing, impossible or inconsistent entries discovered after the data have been transferred to the clinical study database will be referred back to the Investigator using data query forms, and be documented for each individual subject before clean file status is declared.

5.7.3 Genetic data

In the case of genotypic data, only the date the subject gave consent to participation in the genetic research and the date the blood sample was taken from the subject will be recorded in the CRF and database.

The genotypic data generated from the study will be stored in the AstraZeneca LIMS database or other appropriate system. This database is a secure database, which is separate from the database used for the main study. Some or all of the datasets from the main study may be duplicated within the AstraZeneca LIMS database for exploratory genetic analysis.

5.8 Reporting of genotypic results

Results from any genetic research performed will be reported separately from the clinical study report. AstraZeneca will not provide individual genotype results to subjects, their family members, any insurance company, an employer, clinical study investigator, general physician or any other third party, unless required to do so by law. The subject's DNA will not be used for any purpose other than those described in the study protocol.

Individual subjects will not be identified in any report or publication resulting from this work. The data and results of this study may be reviewed with collaborators and published, but neither the subject's name nor any other personal identifiers will appear in any publication or report.

6. PHARMACOKINETIC, SAFETY, AND STATISTICAL METHODOLOGY

6.1 Pharmacokinetic evaluation

6.1.1 Calculation or derivation of pharmacokinetic variables

Pharmacokinetic analyses will be performed by Clinical Pharmacokinetics AstraZeneca, Wilmington, DE.

Tolbutamide and 4-hydroxytolbutamide:

The primary objective will be addressed by estimating C_{\max} and AUC of tolbutamide. The secondary objective will be addressed by estimating C_{\max} and AUC of 4-hydroxytolbutamide. Plasma concentrations of tolbutamide and 4-hydroxytolbutamide will be listed and depicted graphically as a function of time after single-dose administration on Day 5 of both Treatment A and Treatment B. Single-dose pharmacokinetic parameters C_{\max} , t_{\max} , $t_{1/2}$, AUC_{0-t} and AUC of tolbutamide and 4-hydroxytolbutamide and tolbutamide CL/F will be estimated by non-compartmental analysis. C_{\max} will be estimated as the highest measured concentration, and t_{\max} will be the time to maximum concentration following a single dose of tolbutamide. The terminal elimination rate constant (λ_z) will be calculated by log-linear regression of the terminal portion of the concentration-time profile using at least 3 time points. The terminal elimination half-life ($t_{1/2}$) will be calculated as $0.693/\lambda_z$. AUC will be calculated using the linear trapezoidal method up to the last measurable concentration (AUC_{0-t}) and thereafter by extrapolation of the terminal elimination phase to infinity. Tolbutamide CL/F will be estimated as the ratio of tolbutamide dose and AUC. The ratios of 4-hydroxytolbutamide C_{\max} to tolbutamide C_{\max} and 4-hydroxytolbutamide AUC to tolbutamide AUC will be calculated for each treatment.

AZD6140 and AR-C124910XX

Plasma concentrations of AZD6140 and its metabolite AR-C124910XX will be listed and presented graphically as a function of time relative to Day 5 dose. Pharmacokinetic parameters listed below will be estimated by non-compartmental analysis.

Day 4 and 5: steady state $C_{ss,max}$, $t_{ss,max}$ and $AUC_{ss,\tau}$ of AZD6140 and AR-C124910XX, AZD6140 steady state CL/F and metabolite to parent $C_{ss,max}$ and $AUC_{ss,\tau}$ ratios.

AZD6140 and AR-C124910XX $C_{ss,max}$ will be estimated as the highest measured concentration and $t_{ss,max}$ will be the time to maximum concentration within a dosing interval on Days 4 and 5. $AUC_{ss,\tau}$ will be calculated using the linear trapezoidal method over the 12 hour dosing interval on Days 4 and 5, respectively. AZD6140 CL/F in the absence and presence of tolbutamide will be estimated as the ratio of AZD6140 dose and $AUC_{ss,\tau}$ on Days 4 and 5, respectively. The ratio of AR-C124910XX $C_{ss,max}$ to AZD6140 $C_{ss,max}$ ratio and, AR-C124910XX $AUC_{ss,\tau}$ to AZD6140 $AUC_{ss,\tau}$ ratio will be calculated for each treatment.

6.2 Safety evaluation

6.2.1 Calculation or derivation of safety variables

Safety and tolerability will be assessed in terms of incidence and severity of AEs, ECGs, vital signs, and safety blood laboratory assessments.

6.3 Genetics as a co-variate (Not applicable)

6.4 Statistical methods and determination of sample size

Statistical analysis will be carried out by, or under the direction of, Biostatistics at AstraZeneca, Wilmington, using SAS (version 8). Summary graphics required for presentation in the text portion of the CSR will be done using SAS and/or SigmaPlot. Other graphics intended for supplemental figures and individual time plots will be done using SAS.

6.4.1 Statistical evaluation

A comprehensive Statistical Analysis Plan will be prepared and finalized prior to database lock.

6.4.2 Description of variables in relation to hypotheses

In order to assess the effects of multiple doses of AZD6140 on the pharmacokinetics of tolbutamide, C_{max} and AUC of tolbutamide and 4-hydroxytolbutamide will be analysed. To aid in this assessment, t_{max} , AUC_{0-t} and $t_{1/2}$ of tolbutamide and 4-hydroxytolbutamide and tolbutamide CL/F will be computed.

In order to assess the effects of single-dose tolbutamide on the steady-state pharmacokinetics of AZD6140, $C_{ss,max}$ and $AUC_{ss,\tau}$ of AZD6140 and AR-C124910XX will be analysed. To aid in this assessment, $t_{ss,max}$ of AZD6140 and AR-C124910XX and AZD6140 CL_{ss}/F will be computed.

Safety and tolerability will be assessed in terms of incidence and severity of AEs, vital signs, ECGs, clinical chemistry, haematology, urinalysis, and physical examination findings.

6.4.3 Description of analysis sets

Pharmacokinetic Analysis Set: All healthy volunteers who complete both periods of study and for whom evaluable C_{\max} and AUC_{0-t} tolbutamide data was calculated will be included in the formal statistical analysis and the summaries of the pharmacokinetic data.

All available pharmacokinetic data will be listed.

Safety Analysis Set: All healthy volunteers who receive at least one dose study medication will be evaluated for safety.

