Amended Clinical Pharmacology Study Protocol

Drug Substance AZD6140

Study Code D5130C00051

Edition Number 2

Date XXXXXXXXXX

A Randomised, Double-Blind, 2-Period Crossover Study to Assess the Effect of Steady-State AZD6140 on the Pharmacokinetics of a Single Oral 500-mg Dose of Tolbutamide, a Substrate of CYP2C9, in Healthy Male and Female Volunteers

Sponsor: AstraZeneca LP, [name]

AstraZeneca Research and Development
site representative

This submission /document contains trade secrets and confidential commercial information, disclosure of which is prohibited without providing advance notice to AstraZeneca and opportunity to object.

The following Amendment(s) and Administrative Changes are included in this amended protocol:

Amendment No.	Date of Amendment	Local Amendment No.	Date of local Amendment
1		NA	NA
Administrative change No.	Date of Administrative Change	Local Administrative change No.	Date of local Administrative Change

PROTOCOL SYNOPSIS

A Randomised, Double-Blind, 2-Period Crossover Study to Assess the Effect of Steady-State AZD6140 on the Pharmacokinetics of a Single Oral 500 mg Dose of Tolbutamide, a substrate of CYP2C9, in Healthy Male and Female Volunteers

Investigator

Study centre(s), type and number of subjects planned

A single study centre (PAREXEL International, Baltimore, Maryland) will participate in this study. Up to 24 healthy male and female volunteers will be randomised in order to complete at least 18 healthy volunteers.

Study period

Estimated date of first subject enrolled

Estimated date of last subject completed

Phase of development

Clinical Pharmacology-Phase 1

Objectives

The primary objective of this study is:

1. To assess the effect of steady-state AZD6140 on single-dose pharmacokinetics of tolbutamide by analysis of tolbutamide plasma concentrations.

The secondary objectives of this study are:

1. To assess the effect of steady-state AZD6140 on single-dose pharmacokinetics of 4-hydroxytolbutamide by analysis of 4-hydroxytolbutamide plasma concentrations.
2. To assess the effect of a single dose of tolbutamide on steady-state pharmacokinetics of AZD6140 and AR-C124910XX by analysis of AZD6140 and AR-C124910XX plasma concentrations.

3. To examine the safety and tolerability of AZD6140 and a single dose of tolbutamide by assessment of adverse events, 12-lead ECG, vital signs, laboratory parameters and physical examinations.

Study design

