2.2 Secondary objective(s)

The secondary objectives of this study are:

1. To assess the effect of steady-state AZD6140 on single-dose pharmacokinetics of 4-hydroxytolbutamide by analysis of 4-hydroxytolbutamide plasma concentrations.
2. To assess the effect of a single dose of tolbutamide on steady-state pharmacokinetics of AZD6140 and AR-C124910XX by analysis of AZD6140 and AR-C1249XX plasma concentrations.
3. To examine the safety and tolerability of AZD6140 and a single dose of tolbutamide by assessment of adverse events, 12-lead ECG, vital signs, laboratory parameters and physical examinations.

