6.4.5 Determination of sample size

According to published data 12 healthy male healthy volunteers received a single oral 500 mg dose of tolbutamide (Jorga KM, et al. 2000). The inter-subject coefficients of variation (CV) for C_{max} and AUC for these healthy volunteers were estimated to be 27.1% and 33.2%, respectively. Assuming similar variability and an intra-subject correlation of 0.65 (resulting in within-subject CV estimates for C_{max} and AUC of 16% and 20%, respectively), a sample size of 18 healthy volunteers will provide approximately 90% power that the 90% confidence interval for the ratios of interest (C_{max} or AUC) of tolbutamide administered with AZD6140 to that of tolbutamide alone) will be completely contained within the pre-specified equivalence range of 0.80 to 1.25. These calculations are based on a two one-sided testing procedure at an alpha level of 0.05, assuming a true ratio of 1.0. No adjustments for pre-planned multiple comparisons were made.

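### One PK analysis set, defined by completing both periods and by tolbutamide evaluability, excludes valid AZD6140 Day 4/Day 5 pairs from the analysis of secondary objective 2

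*Protocol*

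**What the plan says.** Section 6.4.3 of the protocol has one pharmacokinetic set. It takes "All healthy volunteers who complete both periods of study and for whom evaluable" tolbutamide Cmax and AUC0-t data exist. The same sentence applies this set to the formal analysis and to the PK summaries, with no distinction by analyte. PK data from anyone outside the set are listed only.

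Section 2.2 gives as the second secondary objective: "To assess the effect of a single dose of tolbutamide on steady-state pharmacokinetics of AZD6140 and AR-C124910XX". Section 6.1.1 derives the AZD6140 and AR-C124910XX parameters on Day 4, before tolbutamide, and on Day 5, with tolbutamide. Section 6.4.4 analyses their Css,max and AUCss,τ formally, in the style of the primary endpoints.

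On numbers, the synopsis says: "Up to 24 healthy male and female volunteers will be randomised in order to complete at least 18 healthy volunteers". Section 3.4.3 assigns the two sequences AB and BA in balance. It does not replace dropouts unless too few volunteers look likely to complete.

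**The concern.** Two conditions for entering the set have no bearing on the AZD6140 comparison. AZD6140 is given only in Treatment A, so both halves of the Day 5/Day 4 ratio come from one period, and the sampling for it ends 12 hours after the Day 5 morning dose (Table 5). The placebo period and the tolbutamide assay contribute nothing to that ratio.

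Valid pairs can be lost by two routes:

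- A volunteer in sequence AB completes Treatment A and leaves before or during Period II. The protocol itself creates such exits: Table 1 repeats the drug and alcohol screens on Day -1 of Period II, and under sections 4.3.2 and 4.3.4 a positive result ends participation.
- A volunteer completes both periods but has unevaluable tolbutamide data, for instance in the placebo period.

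In both cases the pair is sound and is left out for a reason unrelated to its quality. What is at stake is precision on a secondary objective, and a set that does not match the comparison it serves.

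**Working it through.** **1. The plan's own figure.** Inputs from section 6.4.5: inter-subject CVs for Cmax and AUC that "were estimated to be 27.1% and 33.2%, respectively"; "an intra-subject correlation of 0.65"; within-subject CVs "of 16% and 20%, respectively"; limits 0.80 to 1.25. "These calculations are based on a two one-sided testing procedure at an alpha level of 0.05, assuming a true ratio of 1.0".

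- Within-subject CV = inter-subject CV × √(1 − 0.65). Cmax: 27.1% × √0.35 = 16.0%. AUC: 33.2% × √0.35 = 19.6%. Both agree with the stated values.
- Power uses standard error σ_w√(2/N), N − 2 = 16 degrees of freedom, and exact integration for the two one-sided tests. For AUC at N = 18 it is 88.8% (CV 20%) or 90.0% (unrounded CV 19.64%). For Cmax (CV 16%) it is 98.3%.

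The protocol's statement, "a sample size of 18 healthy volunteers will provide approximately 90% power", is reproduced. Since about 24 are enrolled so that at least 18 complete, the 18 are completers, which is the population that section 6.4.3 describes.

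**2. How many AZD6140 pairs are left out.** Assumption: 24 randomised (12 AB, 12 BA), 6 leave in the washout, and everyone else is evaluable for everything. A BA volunteer who leaves then has had only placebo and has no AZD6140 pair under any rule. An AB volunteer who leaves then has a complete pair.

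| AB among the 6 leavers | Pairs analysed under 6.4.3 | Pairs available | Left out |
|---|---|---|---|
| 0 | 18 | 18 | 0 |
| 3 (even split) | 18 | 21 | 3 of 21 (14%) |
| 6 | 18 | 24 | 6 of 24 (25%) |

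**3. Effect on the confidence interval.** For a paired log-difference, the 90% CI half-width is t(0.95, n − 1) × σ_w × √(2/n). The within-subject SD cancels in a ratio of widths, so only t/√n matters:

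- n = 18: 0.410
- n = 21: 0.376
- n = 24: 0.350

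0.410/0.376 = 1.09, so 18 pairs give an interval about 9% wider than 21. 0.410/0.350 = 1.17, so about 17% wider than 24.

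**4. In absolute terms.** The protocol gives no within-subject CV for AZD6140. At assumed CVs of 20% and 30%, the multiplicative half-width is 1.122 and 1.186 with 18 pairs, against 1.111 and 1.169 with 21. The difference is real but modest.

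**The case against.** The strongest reply is that a completers set is common in a 2×2 crossover, that all PK data are still listed, and that section 6.4.1 promises a full SAP before database lock, where sets can be refined. For tolbutamide most of this stands. Under the same 3-per-sequence scenario, adding the six one-period tolbutamide profiles to the planned random-subject model lowers the standard error for AUC only from 0.0638 to 0.0624, about 2%. For AZD6140 it does not answer the point, because the comparison is not a crossover comparison. Nor is this a matter left open for the SAP: the protocol states a rule, and an SAP that follows it inherits the problem.

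It is also fair to say that the sizes above are scenarios. Six dropouts is the whole planned allowance, an even split is an assumption, and 17% needs all six to be AB volunteers who leave after Treatment A. The objective has no stated power or limits of its own.

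A reader might infer three stronger things that the documents do not support:

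- *That the set weakens the primary analysis.* The sample size is already set on completers, six extra volunteers are planned, and replacement is allowed. A washout dropout has no tolbutamide pair under any definition.
- *That the loss is biased because withdrawals follow AZD6140 tolerability.* The protocol gives no dropout rates or reasons. Bias in a within-subject ratio would also require tolerability to track the size of the interaction.
- *That anyone leaving late in Period II has an effectively complete tolbutamide profile.* Dosing ends on the evening of Day 9 and the last sample, at 120 hours, is on Day 10. At the label half-life of 6.5 h, 2^(−48/6.5) = 0.6% remains at 48 hours. That is the uninhibited half-life, and the trial tests for inhibition: if it doubled to 13 h (an assumption), 2^(−48/13) is about 8%. Whether such a profile is usable is a question of evaluability, not of calendar completion.

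**Conclusion.** The point holds for AZD6140/AR-C124910XX. Section 6.4.3 makes the analysis of secondary objective 2 conditional on a second period and on tolbutamide results that the comparison does not use. On the assumed pattern of 6 washout leavers, 3 per sequence, 18 pairs are analysed instead of 21 and the 90% CI is about 9% wider, with a range of 0% to 17%. The pairs are excluded from analysis and summaries, not destroyed. The planned primary power is unaffected, and no claim of bias is made.

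For tolbutamide and 4-hydroxytolbutamide the point is minor and concerns wording. Completion is not defined, and the text does not say whether tolbutamide must be evaluable in both treatments, which is what the primary comparison needs.

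**What to change.** Reword section 6.4.3 by analyte:

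- **AZD6140 and AR-C124910XX:** all volunteers with evaluable Day 4 and Day 5 parameters in Treatment A, regardless of Period II completion or tolbutamide evaluability.
- **Tolbutamide and 4-hydroxytolbutamide:** replace the completion requirement with evaluable parameters in both treatments.

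The cost is a short text change, made before unblinding and carried into the SAP. It needs no new data, visits or volunteers. The downside is that n will differ by analyte, so each table must state its own n.
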